### 10.3. Secondary Endpoints

The following secondary efficacy endpoints will be explored:

- S1. Comparison of global haemostatic response to *Octaplex* versus FP, defined as 'positive' if no additional haemostatic intervention (as per the primary endpoint) is required and haemoglobin levels decrease by <30% (after accounting for red cell transfusions) from 60 minutes to 24 hours after initiation of the first dose of IMP. The 24-hour haemoglobin result will be reduced by 1 g/dL for each unit of RBC transfused from 60 minutes to 24 hours.
- S2. Comparison of the total amount of chest tube drainage at 12 and 24 hours after chest closure between the *Octaplex* and FP groups.
- S3. Comparison of the incidence of severe to massive bleeding, using a modification of the universal definition of perioperative bleeding (UDPB) in cardiac surgery and its individual components during the first 24 hours after start of surgery, after the end of CPB and after IMP initiation, between the *Octaplex* and FP groups.
- S4. Comparison of the mean number of total allogeneic blood components – including red cells, platelets and all (IMP and non-IMP) FP – administered during the first 24 hours after the end of CPB, between the *Octaplex* and FP groups.
- S5. Comparison of the mean number of total non-IMP allogeneic blood components – including red cells, platelets and non-IMP FP – administered during the first 24 hours after the end of CPB, between the *Octaplex* and FP groups.
- S6. Comparison of the mean number of total non-IMP allogeneic blood components – including red cells, platelets, cryoprecipitate and non-IMP FP – administered during the first 24 hours and 7 days after IMP initiation, between the *Octaplex* and FP groups.
- S7. Comparison of the mean number of individual allogeneic blood components – including red cells, platelets, cryoprecipitate and non-IMP FP – administered during the first 24 hours and 7 days after the start of surgery, after the end of CPB and after IMP initiation, between the *Octaplex* and FP groups.
- S8. Comparison of the incidence of transfusion of individual allogeneic blood components – including red cells, platelets, cryoprecipitate and non-IMP FP – during the first 24 hours and 7 days after the start of surgery, after the end of CPB and after IMP initiation, between the *Octaplex* and FP groups.

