The analysis of categorical variables (S1, S3, S8, S9, S10, S11, S12) will present relative frequency tables and estimates of the proportions with 95% confidence intervals separately in the treatment groups. The proportions will be compared between the treatment groups in the context of a logistic regression model.

The analysis of continuous variables (S2, S13, S14, S15) will present descriptive statistics of the sampling distribution and the differences between treatment groups. Also, 95% confidence intervals and results of F-test of the treatment group differences will be reported in the context of an ANOVA model.

The analysis of integer count variables (S4, S5, S6, S7) will present descriptive statistics of the sampling distribution and the differences between treatment groups. Treatment group comparisons for variables (S4, S5, S6, S7) will be performed in the context of a counting regression model for the ABCs and their components (SAS PROC GENMOD with Negative-Binomial distribution). Tests and 95% confidence intervals for the treatment group differences will be derived from this statistical model and reported.

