### Transformations to be applied

In order that the sum of Allogenic Blood Products and its constituents adequately represent the exposure to donors, the following transformations will be applied before any derivations:

Platelets	
1 apheresis unit	= 4 allogeneic units,
1 non-apheresis unit	= 4 allogeneic units
Frozen plasma (used in transfusions):	
1 apheresis unit	= 1 allogeneic unit,
1 non-apheresis unit	= 1 allogeneic unit

Transfusion units without any information about apheresis are handled as apheresis units.

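### Counting each platelet unit as 4 before a negative binomial fit inflates the model-based standard error for S7 platelets; the size depends on platelet use that the documents do not give

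*SAP*

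**What the plan says.** SAP Appendix 1, under the transformations, sets one apheresis and one non-apheresis platelet unit each to "4 allogeneic units". For frozen plasma both factors are 1, so of the products listed there only platelets are rescaled. The stated purpose is that "the sum of Allogenic Blood Products and its constituents adequately represent the exposure to donors", which takes in the individual components as well as the totals. On timing, "the following transformations will be applied before any derivations".

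SAP 10.3 defines S7 as "Comparison of the mean number of individual allogeneic blood components", platelets among them, over 24 hours and 7 days from three starting points. S4 to S7 are handled as integer counts, and the comparison of the groups on each of them "will be performed in the context of a counting regression model for the ABCs and their components (SAS PROC GENMOD with Negative-Binomial distribution"). That same model is the source of the inference, since the section goes on to say: "Tests and 95% confidence intervals for the treatment group differences will be derived from this statistical model and reported". No robust variance, scale adjustment or analysis in units as transfused is named. The section opens by saying that "The following secondary efficacy endpoints will be explored".

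**The concern.** Read literally, the S7 platelet variable can take only the values 0, 4, 8, 12 and so on, and these go into a likelihood meant for counts that can be any whole number. The factor 4 cancels in the rate ratio. It does not cancel in the dispersion. The fit has to explain a heap at zero and gaps at 1, 2 and 3, and does so by raising the dispersion beyond what the variance of the data requires.

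At stake is whether the reported interval means what it says. A nominal 95% interval that covers about 98-99% can hide extra platelet use with PCC as easily as a saving. Protocol 3.3.3 names the amount of individual components transfused among the supportive evidence of haemostatic efficacy, so the interval will be read.

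**Working it through.** **Inputs from the documents.** Factor 4; negative binomial model; model-based tests and intervals; at least 205 evaluable patients per arm (Protocol 4.1). The plan's own sample size reproduces: (1.960 + 1.282)² × (0.65 × 0.35 + 0.70 × 0.30) / (0.05 + 0.10)² = 10.507 × 0.4375 / 0.0225 = 204.3, so 205 per arm and 410 in all. A Farrington-Manning check gives 90.1% power. The documents state no standard error, interval width or power for S7 platelets.

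**Assumed, not in the documents.** FP-arm mean of 0.5 to 3 platelet doses (dose = unit as transfused), dispersion k of 0 to 2, rate ratio mostly 0.75, and some hand-set distributions with chosen shares of zeros.

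**Formula.** For two arms with fitted means m, common dispersion k and n per arm, SE(log ratio) = √[Σ(1/m + k)/n].

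**Why scale matters.** If doses have mean μ and variance μ + kμ², then 4 × doses has mean 4μ and variance 16μ + 16kμ². To match that variance, the dispersion on the ×4 scale should be k + 3/(4μ). Then 1/(4μ) + k + 3/(4μ) = 1/μ + k, and the standard error would be right. Maximum likelihood does not give that value. With k = 0.5 and means 1.0 and 0.75, matching needs 1.25 and 1.50; the large-sample fit gives 2.711.

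**Worked case (means 1.0 and 0.75, k = 0.5).**
- In doses: √[(1.500 + 1.833)/205] = 0.1275.
- ×4: √[(0.250 + 2.711 + 0.333 + 2.711)/205] = 0.1712.
- Ratio: 0.1712/0.1275 = 1.34.
- Power, with |ln 0.75| = 0.2877 and true SE 0.1275: in doses Φ[(0.2877 − 1.96 × 0.1275)/0.1275] = 0.62; ×4 Φ[(0.2877 − 1.96 × 0.1712)/0.1275] = 0.35.

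**Range, k = 0.5, rate ratio 0.75.**

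| FP mean (doses) | Excess width | Power, doses | Power, ×4 |
|---|---|---|---|
| 0.5 | 44% | 0.41 | 0.14 |
| 1.0 | 34% | 0.62 | 0.35 |
| 1.5 | 28% | 0.73 | 0.53 |
| 2.0 | 23% | 0.80 | 0.65 |
| 3.0 | 17% | 0.87 | 0.79 |

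Over the whole negative binomial and Poisson grid the excess is 11-45%.

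**Hand-set distributions.**

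| Zeros FP / PCC | Means | Excess width | Power, doses | Power, ×4 |
|---|---|---|---|---|
| 15% / 20% | 1.71 / 1.35 | 9% | 0.82 | 0.78 |
| 25% / 32% | 1.52 / 1.21 | 21% | 0.66 | 0.50 |
| 40% / 48% | 1.16 / 0.91 | 31% | 0.51 | 0.28 |
| 60% / 68% | 0.70 / 0.52 | 39% | 0.42 | 0.16 |

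Four further distributions with 10-25% zeros put the ×4 standard error 2-16% above its true value.

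**Strong effects.** At mean 1.0 and k = 0.5, power falls from 0.97 to 0.88 at ratio 0.6, and from 0.999 to 0.991 at ratio 0.5.

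**Simulation (1,500 trials per setting, negative binomial doses).** The ×4 fit had type I error 0.6-1.9% and coverage 98.1-99.4%. The fit in doses had 4.2-5.7% and 94.0-95.9%.

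**Totals.** An assumed S5 total had a standard error about 6-7% too large. S4 and S6 were not quantified.

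**Robust errors.** With treatment as the only term, the sandwich variance of a log mean is about s²/(n m²). Multiplying the data by 4 multiplies s² and m² by 16 each, so the result does not move. In the cases tried, robust errors stayed within about 5% of the true standard deviation.

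**The case against.** The mechanism is not in dispute; the size is. A reader might infer from mid-range scenarios that the platelet interval is 23-38% too wide and that the comparison loses a large part of its power. The documents do not support that as a statement about this trial, because both figures rest on a platelet mean, dispersion, share of zeros and effect that are nowhere given.

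The pilot data in Protocol 1.1 speak against the upper end. In the PCC group the lower quartile of total units was 4, the upper quartile of red cells was 2, and 3.7% needed FP. If both quartiles refer to the same 24 hours, at least 75 − 25 − 3.7 = 46.3% of PCC patients received platelets, however units were coded. The 44% case implies only 1 − (1 + 0.5 × 0.375)⁻² = 29%. The 34% case implies 1 − (1 + 0.5 × 0.75)⁻² = 47%, which just fits. So excesses much above a third sit poorly with the pilot, though that was 54 PCC patients at two hospitals.

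Three further points stand. The endpoints are exploratory with no power target, and an over-wide interval creates no false claim. S8 compares the incidence of platelet transfusion over the same windows by logistic regression, which the factor cannot affect; it does not, however, address the amount. And modelling doses is not a complete cure. In two cases with underdispersed dose counts, the negative binomial fit in doses overstated the standard error by 10% and 19%, against 6% and 8% on the ×4 scale. That is a reason to rely on robust errors, not to leave the plan as it is.

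**Conclusion.** The point holds as a specification defect of uncertain size. The SAP as written gives S7 platelets a model-based standard error that depends on an arbitrary unit of display. With 205 per arm and assumed platelet distributions, the excess in standard error or interval width runs from a few percent to about 45%. The loss of power runs from under 1 to about 30 points, and is small for strong effects or few zeros.

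The test is conservative for negative binomial doses and for distributions with a moderate share of zeros. That direction should not be taken as guaranteed if nearly every patient receives platelets. S4 to S6 share the defect in weaker form. The rate ratio, the descriptive summaries, S8 and the primary non-inferiority test are unaffected.

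**What to change.** In SAP 10.3, state that tests and 95% confidence intervals for S4 to S7 use robust (sandwich) standard errors, through the REPEATED statement in PROC GENMOD with the patient as subject. For S7 platelets these do not depend on the factor 4.

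Preferably also state in Appendix 1 that the S7 platelet model is fitted to units as transfused, with the factor 4 kept for the totals and for displayed donor-exposure means. Keep the robust errors there too, because dose counts may be underdispersed. The platelet rate ratio is the same either way.

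The cost is a sentence or two in the SAP and a small programming change. It should be made before any unblinded analysis of these endpoints.

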## 10.4. Sensitivity Analyses

The analysis results for the primary endpoint will be presented in different contexts. This will include those involving the different multiple imputation procedures for missing data, if needed. The analysis of the primary endpoint will be presented for the PPS. Haemostatic treatment response will also be summarized descriptively by study site.

## 11. Safety Analysis

All safety analyses will be based on the FAS population. If the SAF population differs from the FAS population, then only AE information will additionally be displayed for the SAF.

All AEs and SAEs will be collected from beginning of surgery (defined as entry into OR) to POD-30.

The analysis of safety will study the following endpoints:

1. Comparison of the incidence of serious treatment-emergent adverse events (TEAEs), individually and as composite where appropriate (e.g., TEEs and MACE), between the *Octaplex* and FP groups.
2. Comparison of the duration of mechanical ventilation (measured as duration of ventilation and ventilator-free days) up to POD-30 between the *Octaplex* and FP groups.
3. Comparison of the duration of initial ICU stay up to POD-30 between the *Octaplex* and FP groups.
4. Comparison of the duration of hospitalisation up to POD-30 between the *Octaplex* and FP groups.
5. Comparison of the incidence of death up to POD-30 between the *Octaplex* and FP groups.
6. Comparison of the number of days alive and out of hospital at POD-30 between the *Octaplex* and FP groups.

### 11.1. Adverse events

AEs will be coded according to the MedDRA. Coding will be agreed upon with the Sponsor before database lock (cf. DMP).

All AEs recorded for patients in the SAF will be listed in the appendix of the study report, differentiated by treatment-emergent and non-treatment-emergent AEs.

Only treatment-emergent AEs (TEAE) will be analysed, i.e., all new and worsening pre-existing AEs occurring after first IMP administration up to POD-30. It is assumed that for each increase in intensity of an AE a new entry of the AE will be recorded by the investigator; hence, such cases will be analysed like different phases of the same AE.

A descriptive analysis will be performed. This analysis will comprise the following set of tables, separated by treatment group and time of first occurrence (within 48 hours, 7 days and 30 days post-surgery):

- Global incidence
- Incidences by primary system organ classes (SOC) and incidences of preferred term within primary SOC sorted according to the Internationally Agreed Order

Global incidences of primary SOC and preferred terms will be calculated for

- All TEAE irrespective of the causality assessment
- TEAE by relationship (probable, possible, unlikely, not related and unclassified)
- TEAEs by worst severity
- Serious TEAEs
- TEAEs possibly or probably related per PI assessment
- TEAEs possibly or probably related per sponsor assessment
- TEAEs possibly or probably related per PI and/or sponsor assessment
- TEEs per PI assessment
- TEEs per MedDRA SMQ
- TEEs per sponsor assessment
- Treatment-emergent major adverse cardiac events (MACE)

Multiple counts within a preferred term or SOC (repeated or different included terms or changes in descriptors) will be counted only once for the calculation of incidences.

A listing of 'special cases' containing patient ID, age, sex, AE descriptors and start and end of treatment will be prepared for the following types of TEAEs:

- Fatal SAEs
- AEs which led to discontinuation
- Myocardial infarction
- Stroke
- Acute liver injury
- Acute kidney injury
- TEEs
- MACE
- TRALI
- TACO

The number of patients who died will be summarised. A possible difference between treatment groups will be estimated by the risk ratio with 95% confidence interval. Kaplan-Meier estimates for the time to death distribution will be calculated and graphically presented. The incidence of death up to POD-30 will be calculated, as well as the incidence of death within 48 hours or 7 days, and special cause mortality.

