The non-inferiority of the primary endpoint 'haemostatic response' will be tested between the treatment groups by means of a Farrington-Manning score test with a non-inferiority margin of 0.10. At the end of the trial, the inverse normal test statistic with equal weights given by $(\Phi^{-1}(1 - p_1) + \Phi^{-1}(1 - p_2))/\sqrt{2}$ is calculated, where p_1 and p_2 denote the p-values for testing the non-inferiority null hypothesis for the first and the second stage of the trial, respectively. If the test statistic exceeds the value 1.96, non-inferiority is demonstrated. Only in case that non-inferiority is demonstrated, i.e., the null hypothesis is rejected at the one-sided 2.5% level of significance, superiority of PCC with regard to the primary endpoint will be investigated.

Descriptive statistics or frequency tables will be presented for all efficacy and safety data in addition to the inferences performed. The summary tables and exploratory inferences will be chosen according to the scaling level of the measurements, e.g., frequency tables for categorical responses, sampling statistics for continuous data. Safety endpoints will be analysed analogously to the primary endpoint, presenting point estimates and two-sided 95% CIs in addition to descriptive statistics. The Statistical Analysis Plan (SAP) will detail all analyses to be undertaken prior to study initiation.

The full analysis set (FAS) will consist of all consented and randomised patients who receive any amount of the intervention, which will serve as the primary analysis set. A secondary efficacy analysis will be performed for the per-protocol set (PPS), which will exclude all patients with major deviations. Consented, randomised but untreated patients will not be included in the efficacy or safety analyses, but will be followed for 30 days to determine between-group comparability in baseline characteristics and outcomes.

FLOW CHART OF ASSESSMENTS

Table 1: Flow Chart of Assessments Performed Throughout the Study

ASSESSMENTS	Screening visit (≤28 days before surgery)	Visit 1 POD 0 Pre-randomisation visit (blood bank/pharmacy)	Visit 2 POD 0-1 First visit after IMP initiation (0 to 24 h after IMP initiation) ¹	Visit 3 POD 2-7 after IMP initiation (or at discharge if earlier)	Visit 4 POD 30 after IMP initiation (in person if in hospital, or by phone)
Patient consent	X				
Inclusion and exclusion criteria	X ²	X			
Blood bank/pharmacy receives PCC or FP order ³		X			
Body weight		X			

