3.1.3 Safety Endpoints

All AEs and serious AEs (SAEs) will be collected from beginning of surgery (defined as entry into OR) to POD-30.

1. Comparison of the incidence of serious treatment-emergent adverse events (TEAEs), individually and as composite where appropriate (e.g., TEEs, major adverse cardiac events), between the *Octaplex* and FP groups.
2. Comparison of the duration of mechanical ventilation (measured as duration of ventilation and ventilator-free days) up to POD-30 between the *Octaplex* and FP groups.
3. Comparison of the duration of ICU stay up to POD-30 between the *Octaplex* and FP groups.
4. Comparison of the duration of hospitalisation up to POD-30 between the *Octaplex* and FP groups.
5. Comparison of the incidence of death up to POD-30 between the *Octaplex* and FP groups.
6. Comparison of the number of days alive and out of hospital at POD-30 between the *Octaplex* and FP groups.

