9.2.3 Safety Analysis Plan

Secondary safety endpoints will be analysed analogously to the primary endpoint, presenting point estimates and two-sided 95% CIs in addition to descriptive statistics. Prior to study initiation, the SAP will detail all analyses to be undertaken.

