### **7. Statistical Methods**

All statistical analyses will be performed using the SAS® software (Version 9.4 or later).

The analysis of safety will be based on the FAS population.

The primary evaluation of overall efficacy will be performed on the FAS population. In addition, selected efficacy analyses will also be presented for the PPS population.

If not stated otherwise, the following standard descriptive statistics will be presented:

- Descriptive statistics for continuous data

Number (N), mean, standard deviation (SD), min, lower quartile, median, upper quartile and max will be presented. These descriptive statistics will be determined for measured values and optionally for differences to baseline.

- Descriptive statistics for categorical data

Absolute frequencies and percentages will be presented. Percentage bases (denominators) will be identified in the table title or footnote (i.e., all patients at risk, all non-missing cases, all cases). For changes from baseline, shift tables may be generated.

- Exploratory statistics

Although statistical methods are primarily descriptive, two-sided 95% confidence intervals may be presented for selected parameters (e.g., incidences of adverse events) in an exploratory manner.

- Listings

All recorded data will be listed by patient. Identification variable will be the patient ID.

Derived data will be stored in special analysis data sets and will be calculated as outlined in **Appendix 1**.

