## 14. Changes from Analyses Specified in the Protocol

The described statistical analyses match those pre-specified in the study protocol.

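### Safety endpoint 1 names a between-arm comparison of serious TEAEs, TEEs and MACE, but the plan commits only to incidence tables by arm, with no estimate and confidence interval

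*SAP*

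**What the plan says.** Protocol 9.2.3 gives the rule: "Secondary safety endpoints will be analysed analogously to the primary endpoint, presenting point estimates and two-sided 95% CIs in addition to descriptive statistics". The statistical part of the synopsis says the same without the word 'secondary'. Safety endpoint 1 (protocol 3.1.3) begins "Comparison of the incidence of serious treatment-emergent adverse events (TEAEs), individually and as composite where appropriate (e.g., TEEs, major adverse cardiac events", and SAP 11 restates it as a comparison between the two groups.

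The methods given for these events are narrower:

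- **Protocol 9.2.3.1**, the subsection on adverse events including thromboembolic events, plans summaries and frequency tables, with separate tables for TEEs (identified by MedDRA SMQ) and composite events.
- **SAP 11.1** says "A descriptive analysis will be performed", and then "This analysis will comprise the following set of tables, separated by treatment group and time of first occurrence". Serious TEAEs, TEEs under three definitions (investigator, SMQ, sponsor) and MACE are on the list.
- **SAP 7** adds that "two-sided 95% confidence intervals may be presented for selected parameters (e.g., incidences of adverse events) in an exploratory manner".

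Death is treated differently. Protocol 9.2.3.2 and the end of SAP 11.1 both commit to a risk ratio with a 95% CI. SAP 14 states: "The described statistical analyses match those pre-specified in the study protocol".

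**The concern.** Secondary objective 11 is to compare the arms on serious TEAEs, and the endpoint names TEEs and MACE as its composites. Two percentages side by side do not make that comparison. They give no size of difference and no range of differences compatible with the data. Protocol 1.1 raises the possibility of more thrombotic events with PCC at high doses, and answers it partly by calling pilot TEE rates of 7.4% and 8.2% similar. Tables without an interval invite the same reading of this trial, which is large enough to say something more exact.

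There is also a pre-specification issue. An optional interval, with no contrast, effect measure or TEE definition fixed, leaves those choices open until results are known.

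**Working it through.** **1. Passages side by side**

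| Place | Serious TEAEs, TEEs, MACE | Death |
|---|---|---|
| Protocol synopsis and 9.2.3 (general rule) | Estimate and 95% CI, plus description | Same |
| Protocol 9.2.3.1 / 9.2.3.2 (specific) | Tables | Risk ratio with 95% CI |
| SAP 7 (general) | CI optional, no contrast named | CI optional |
| SAP 11.1 (specific) | Tables by arm and time window | Risk ratio with 95% CI |

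The general rule asks for estimates in addition to description, so the tables in 9.2.3.1 do not by themselves satisfy it. The word 'secondary' in 9.2.3 does not take endpoint 1 out of scope. The synopsis has no such limit, and objective 12 goes on to 'other' secondary safety endpoints after serious TEAEs in objective 11. SAP 11.1 follows the specific subsections and leaves the general rule unmet.

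**2. The plan's own figure**

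The documents give no precision target for safety endpoint 1. The design figure that sets the arm size is 410 evaluable patients. With 70% versus 65%, margin 0.10, one-sided 0.025 and 90% power, the Farrington-Manning formula gives 205 per arm (410 in total), with 90.1% power. The stated number is reproduced. The maximum in the sample-size table is 1000 evaluable patients, or 500 per arm.

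**3. Width of the missing interval**

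Assumption: about 8% TEEs in each arm, close to the pilot's 7.4% and 8.2%. Both stages are pooled.

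Simple (Wald) half-width: 1.96 × √(2 × 0.08 × 0.92 / n).

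- n = 205: 5.25 points
- n = 500: 3.36 points

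The score interval contains every d for which |p̂₁ − p̂₂ − d| / √(q₁(1−q₁)/n + q₂(1−q₂)/n) ≤ 1.96, where q₁ and q₂ are the maximum-likelihood estimates under q₁ − q₂ = d.

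- 16/205 versus 16/205 (7.8% each): −5.4 to +5.4 points
- 40/500 versus 40/500 (8.0% each): −3.4 to +3.4 points

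At the smaller size, identical rates would still leave open an excess of 5.4 points on a base of 7.8%. Since 5.4/7.8 = 0.69, that is about two thirds of the base rate.

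With the pilot rates themselves (Wald for the difference, log scale for the ratio):

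| Per arm | Risk difference, points (95% CI) | Risk ratio (95% CI) |
|---|---|---|
| 205 | −0.8 (−6.0 to +4.4) | 0.90 (0.46 to 1.76) |
| 500 | −0.8 (−4.1 to +2.5) | 0.90 (0.59 to 1.38) |

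**4. Why a CI for each arm is no substitute**

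Constructed example, not a forecast: 30/205 (14.6%) versus 17/205 (8.3%). The Wilson intervals for the arms overlap (10.4–20.1% and 5.2–12.9%), yet the score interval for the 6.3-point difference is 0.2 to 12.7. SAP 7 refers to intervals for incidences. Even if that option is used, the between-arm question may stay unanswered.

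**The case against.** The strongest reply is that SAP 11.1 does what the protocol's own adverse-event subsection asks. Protocol 9.2.3.1 plans tables for serious TEAEs, TEEs and composites, 9.2.3.2 gives a between-arm estimate for death only, and the SAP mirrors both. This stands. A reader might infer that the SAP cut back an analysis the protocol had specified for these events. The documents do not support that: the protocol holds a general rule and a narrower subsection, and the SAP leaves the two unreconciled. For the same reason, SAP 14 is better described as incomplete than as plainly false.

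Second, intervals are not ruled out. SAP 7 permits them and gives adverse-event incidences as its example, and SAP 13 leaves the full output list to a separate document that is not available here. So it would be wrong to say that no CI will appear; the supportable statement is that the SAP text commits to none.

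Third, counts by arm will be reported, so any reader can derive a difference and its interval. True, but that does not fix the contrast or the TEE definition in advance.

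Fourth, adverse-event reporting is usually descriptive. That is sensible for system organ class and preferred-term tables. It is less so for the few outcomes that the endpoint itself names for comparison.

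**Conclusion.** The point holds in a limited form: for serious TEAEs, TEEs and MACE the between-arm comparison is named as an endpoint, and required by the protocol's general rule, but not committed in the analysis text. It is worth correcting because the correction is nearly free and lets the trial answer the question that endpoint 1 asks. It does not affect the primary endpoint, type I error, power or sample size.

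Two further readings go beyond the documents. One is that the case for approval rests on showing no extra thrombotic risk; the documents do not say so, and they set no safety hypothesis, margin or power. The other is that a risk difference is the only faithful measure. 'Analogously to the primary endpoint' points towards a difference in proportions, but the protocol's own contrast for death is a risk ratio, so either is consistent with it.

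The widths of about ±5.4 points (205 per arm) and ±3.4 points (500 per arm) rest on the assumed 8% TEE rate in each arm. The pilot rates give similar widths.

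**What to change.** In SAP 11.1, commit to a between-arm estimate (PCC versus FP) with a two-sided 95% CI, up to POD-30, for three outcomes:

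1. serious TEAEs;
2. TEEs by the MedDRA SMQ, the definition in protocol 7.3.5 and 9.2.3.1, with the investigator and sponsor versions remaining as tables;
3. treatment-emergent MACE.

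Name one measure in advance: a risk difference with a score CI, in line with the primary endpoint, or a risk ratio with CI, as for death. In SAP 7, make the interval mandatory for these three outcomes. Keep all other adverse-event tables descriptive. If the sponsor prefers tables only, SAP 14 should say that this departs from the general rule in protocol 9.2.3.

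The cost is a wording change and three extra estimates, with no new data. The downside is that the intervals will be visibly wide, especially at the minimum sample size.

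In the same revision, the sponsor should check safety endpoints 2 to 4 and 6 (ventilation, ICU stay, hospital stay, days alive and out of hospital). SAP 11 lists them as comparisons but gives no between-arm method.
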